#### **4.1.3. Rationale for Use of Pembrolizumab in Small Cell Lung Cancer in the Second Line Setting**

Therapeutic options remain limited in SCLC, and more effective therapies are critically needed.

As SCLC is characterized by immunogenic effects and an exceptionally high degree of genomic alterations due to tobacco carcinogens, immune checkpoint blockade utilizing pembrolizumab warrants further exploration in this disease. Evaluating pembrolizumab in the second line setting is appropriate given the early data available demonstrating its activity in SCLC.

## **4.2. RATIONALE FOR DOSE SELECTION/REGIMEN/MODIFICATION**

### **4.2.1. Pembrolizumab and rationale for its Dose Selection**

Pembrolizumab will be provided by Merck. Pembrolizumab 200 mg will be administered as a 30 minute IV infusion every 3 weeks.

An open-label Phase I trial (KEYNOTE 001) is being conducted to evaluate the safety and clinical activity of single agent pembrolizumab (MK-3475). The dose escalation portion of this trial evaluated three dose levels, 1 mg/kg, 3 mg/kg, and 10 mg/kg, administered every 2 weeks in patients with advanced solid tumors. All three dose levels were well tolerated and no dose-limiting toxicities were observed. This first in human study of pembrolizumab (MK-3475) showed evidence of target engagement and objective evidence of tumor size reduction at all dose levels (1 mg/kg, 3 mg/kg and 10 mg/kg every 2 weeks). No maximum tolerated dose has been identified to date. Recent data from other clinical studies within the pembrolizumab (MK-3475) program has shown that a lower dose of the agent and a less frequent schedule may be sufficient for target engagement and clinical activity.

Pharmacokinetic (PK) data analysis of pembrolizumab (MK-3475) administered every 2 weeks and every 3 weeks showed slow systemic clearance, limited

volume of distribution, and a long half-life (refer to Investigator's Brochure, IB). Pharmacodynamic data (IL-2 release assay) suggested that peripheral target engagement is durable (>21 days). This early PK and pharmacodynamic data provides scientific rationale for evaluating both an every 2 week and every 3 week dosing schedule.

A population pharmacokinetic analysis has been performed using serum concentration time data from 476 patients. Within the resulting population PK model, clearance and volume parameters of pembrolizumab (MK-3475) were found to be dependent on body weight. The relationship between clearance and body weight, with an allometric exponent of 0.59, is within the range observed for other antibodies and would support both body weight normalized dosing or a fixed dose across all body weights. Pembrolizumab (MK-3475) has been found to have a wide therapeutic range based on the melanoma indication. The differences in exposure for a 200 mg fixed dose regimen relative to a 2 mg/kg every 3 weeks body weight based regimen are anticipated to remain well within the established exposure margins of 0.5 – 5.0 for pembrolizumab/MK-3475 in the melanoma indication. The exposure margins are based on the notion of similar efficacy and safety in melanoma at 10 mg/kg every 3 weeks vs. the proposed dose regimen of 2 mg/kg every 3 weeks (i.e. 5-fold higher dose and exposure). The population PK evaluation revealed that there was no significant impact of tumor burden on exposure. In addition, exposure was similar between the NSCLC and melanoma indications. Therefore, there are no anticipated changes in exposure between different indication settings.

The choice of the 200 mg every three weeks as an appropriate fixed dose is based on simulations performed using the population PK model of pembrolizumab showing that the fixed dose of 200 mg every 3 weeks will provide exposures that 1) are optimally consistent with those obtained with the 2 mg/kg dose every 3 weeks, 2) will maintain individual patient exposures in the exposure range established in melanoma as associated with maximal efficacy response, and 3) will maintain individual patients exposure in the exposure range established in melanoma that are well tolerated and safe.

A fixed dose regimen will simplify the dosing regimen to be more convenient for physicians and to reduce potential for dosing errors. A fixed dosing scheme also will reduce complexity in the logistical chain at treatment facilities and reduce wastage.

#### **4.2.2. Topotecan and Rationale for its dose selection**

Topotecan is manufactured by GlaxoSmithKline and is commercially available. Topotecan will be administered intravenously at 1.25 mg/m^2 on days 1 to 5 of each 3 week (21-day) cycle. This dose has been selected to mitigate the hematologic toxicities associated with topotecan at the initially studied dose of 1.5 mg/m^2, while preserving its efficacy.

This 1.25 mg/m^2 dose was evaluated in a prospective multicenter trial to determine whether it could improve safety in patients with relapsed/ refractory small cell lung cancer without loss of efficacy. In this study, patients

received topotecan intravenously on days 1–5, every 21 days, for up to six courses. For those patients who did not incur toxicities, topotecan was increased to 1.5mg/m^2; yet in those with severe side effects, the dose was reduced to 1.0 mg/m^2. Severe toxicities were considered grade 4 neutropenia lasting greater than 7 days; grade 4 thrombocytopenia or platelet count < 100,000/mm^3 and neutrophils < 1500/mm^3; or any grade 3 or 4 non-hematologic toxicity besides alopecia, nausea and emesis. A total of 514 topotecan courses were received by 164 patients; in 72.6% of those courses, the dose remained at 1.25 mg/m^2; in 9.1% it was reduced and in 18.3% it increased. Toxicities seemed to be less for the patients treated at the 1.25 mg/m^2 dose when compared to historical data, as grade 4 neutropenia and thrombocytopenia occurred in 7% and 5% of courses, with mild non-hematologic toxicities. Efficacy was maintained as the overall response rate for all patients (sensitive and refractory) was 14.1% and median survival was 23.4 weeks. Therefore, topotecan at a dose of 1.25 mg/m^2 was found to be as effective as the dose of 1.5 mg/m^2, but with reduced toxicity. As such, we have chosen this dosing schedule for this study.

## **5. RATIONALE FOR ENDPOINTS**

### **5.1. EFFICACY ENDPOINTS**

#### **5.1.1. Primary**

This randomized phase II study will assess progression free survival (PFS) as the primary endpoint based on RECIST 1.1. Given the cross-over design, PFS as opposed to overall survival was considered to be an acceptable scientific endpoint to identify the best treatment for SCLC patients in need of second-line therapy. According to the findings from the phase III study studying topotecan vs CAV in the second-line treatment of SCLC patients and the phase III trial comparing oral and intravenous topotecan, we expect only a median PFS of 12 weeks for the control arm. Further, it is anticipated that the SCLC patients responding to pembrolizumab will have a longer duration of response, which will be assessed by RECIST 1.1. The PFS rate at 6 and 9 months in each group will be assessed and compared.

#### **5.1.2. Secondary**

[figure not shown]
The objective response rate (ORR) will be determined in each arm of the study by RECIST 1.1. Notably, topotecan leads to a differential response in SCLC patients with sensitive vs refractory disease, which we do not anticipate in those receiving pembrolizumab. With the cross-over design, we will be able to determine the ORR for pembrolizumab in the second- and third-line setting. Overall survival of patients in each arm of the study will be analyzed. The treatment-related toxicity of pembrolizumab and topotecan will be summarized by toxicity type and grade for each treatment arm.

## 5.2. EXPLORATORY ENDPOINTS; BIOMARKERS OF RESPONSE TO IMMUNE CHECKPOINT INHIBITORS

### 5.2.1. PD-L1 Tumor Expression

Tumor PD-L1 expression levels extensively have been evaluated to determine potential associations with response to pembrolizumab. In Keynote-001, 449 patients with previously treated non-small cell lung cancer patients (NSCLC) received pembrolizumab at 2mg/kg (N = 55) and at 10 mg/kg (N = 394). The anti-PD-L1 antibody clone 22C3 (Merck) and a prototype immunohistochemical assay was used to determine PD-L1 status. PD-L1 positivity was defined as membranous staining in at least 1% of cells (neoplastic and intercalated mononuclear inflammatory cells) within tumor nests or a distinctive staining pattern caused by the infiltration of mononuclear inflammatory cells in the stroma that formed a banding pattern adjacent to tumor nests. A tumor proportion score (TPS) was assigned to each sample based on the percentage of tumor cells with membranous PD-L1 staining.

**Figure 3. PD-L1 Expression**

[figure not shown]

Response rates significantly were higher in patients whose samples demonstrated a TPS  $\geq$  50%. Further, patients with higher PD-L1 expression seemed to have a faster time to response. Median overall survival was 15.5 months (95% CI, 10 – NR) in patients with TPS  $\geq$  50% compared to 11.3 months (95% CI, 8.8 – 14.0) in all patients.

In Keynote-028, PD-L1 expression was necessary for SCLC patients to be eligible, as described above. One-hundred forty seven samples were evaluable for PD-L1, of which 42 (29%) displayed  $\geq$ 1% PD-L1 positivity in tumor, inflammatory cells or stroma. Subsequently, 24 patients were treated according to protocol who had received one or more prior lines of therapy for SCLC. Notably, there was no relationship between the extent of PD-L1 positivity and the frequency of responses.

### 5.2.2. Smoking Status, Smoking-Related Genotoxicity, and Mutation Burden

We and others have shown that smokers with lung cancers are most likely to benefit from PD-1 blockade. In 495 patients with NSCLCs treated with pembrolizumab, the response rate was 22.5% in smokers compared to 10.3% in never smokers. We hypothesize this differential response is related to the increased mutational burden found in smoking-related cancers. To examine this hypothesis, we have performed whole exome sequencing of 34 NSCLC patients treated with pembrolizumab; higher mutational burden was associated with a more durable response to pembrolizumab and an improvement in progression-free survival (PFS) compared to those with lower mutation burden. We also applied a molecular classifier of smoking-related genotoxicity, which distinguishes genomes characteristic of lung cancers in smokers (defined by a predominance of C>T transversions, termed "transversion-high" or TH, smoking signature) from the genomic alterations characteristic of lung cancers in never smokers (transversion low, TL, non-smoking signature). TH-tumors were highly associated with response and improved PFS to pembrolizumab. Moreover, TH-tumors were highly associated with mutation burden, suggesting that the molecular smoking signature may be able to identify those patients with the greatest mutation burden and most likely to benefit from pembrolizumab. The association between response to pembrolizumab, mutation burden, and molecular smoking history is highly applicable to SCLC as this disease is nearly entirely related to smoking and characterized by an elevated mutation burden.

The critical link in understanding the association between mutation burden and response to T cell checkpoint inhibitors may be neoantigens. Neoantigens are cancer-specific novel immunogenic peptides resulting from somatic, non-synonymous mutations in tumor cells, which when presented by class I or II MHC molecules, can be targets for T-cell recognition and effector responses. Whole exome sequencing and computational neoantigen prediction also have been performed on a series of melanomas from patients treated with ipilimumab. Responders to ipilimumab were characterized by an elevated mutation burden and neoantigen-specific T cell responses were identified in the peripheral blood of three long-term responders to ipilimumab. We also have begun to explore the neoantigen landscape associated with response to pembrolizumab in NSCLC: responders have a greater absolute burden of neoantigens. Additionally, in one patient with a near complete response to pembrolizumab, we identified a neoantigen-specific T cell response in the peripheral blood that corresponded with clinical response to anti-PD-1 therapy. This case is suggestive that responses to anti-PD-1 therapy may be mediated by expansion of neoantigen-specific T cell clones and that neoantigen-based peripheral blood monitoring may provide an opportunity to examine and monitor response to PD-1 therapy.

## 6. OBJECTIVES

### 6.1. PRIMARY OBJECTIVE

To demonstrate an improvement in progression free survival (PFS) in patients with relapsed sensitive or refractory SCLC receiving pembrolizumab compared to topotecan, utilizing RECIST 1.1.

### 6.2. SECONDARY OBJECTIVES

- i. Determine the objective response rate (ORR) in each arm of the study by RECIST 1.1.
- ii. Determine the overall survival (OS) of patients in each arm of the study.
- iii. Determine the ORR, and OS of pembrolizumab and topotecan, in the following patient groups:
  - a. Sensitive disease vs. Refractory disease
- iv. Determine the safety and tolerability of pembrolizumab in patients with SCLC.

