### 19.1. SAMPLE SIZE JUSTIFICATION

According to the findings from the phase III study studying topotecan vs CAV in the second-line treatment of SCLC patients and the phase III study comparing oral and intravenous topotecan, we expect a median PFS of 12 weeks for the control arm (C) and 20 weeks (a 67% increase) for the experimental therapy (E) in the pooled patient population with relapsed sensitive or refractory SCLC. Under the assumption of exponential survival time, it corresponds to a hazard ratio  $\lambda_E/\lambda_C = 0.60$ . Assuming an accrual rate of 4 randomized patients per month, it will take approximately 23 months to enroll 93 randomized patients (62 arm E and 31 arm C). With additional follow-up of 26 weeks (approximately 6 months) after the enrollment of the last patient, or approximately 86 events (59 arm E, 27 arm C), the study has approximately 82% power to reject the null hypothesis  $\lambda_E/\lambda_C = 1$  and accept the alternative hypothesis  $\lambda_E/\lambda_C < 1$  when the true  $\lambda_E/\lambda_C = 0.60$  using a stratified log rank test at a 1-sided significance level of 0.10.

Per above, eligible patients will be randomized with 2:1 allocation to two arms (E and C). The patients on arm C are allowed to receive pembrolizumab after progression. The final analysis is expected to take place 6 months after the last enrolled patient has been treated.

In the primary analysis, a stratified log rank test with equal weights over time will be used to test the PFS difference between two arms. As late treatment effect is often observed for immunotherapy, a weighted log rank test with Fleming-Harrington weights also will be used as a supplementary analysis to maximize the test efficiency for late treatment effect. More details can be found in the Analytic Method section.

Objective response rate (ORR) is a secondary endpoint. The sample size of the study is not determined by having adequate power to test ORR. With 62/31 patients on arm E/C, the study has approximately 82% power to differentiate  $ORR < 12\%$  versus  $ORR > 32\%$  at one-sided significance level of 0.10

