## 20. STATISTICAL ANALYSIS PLAN

The primary analysis will include all randomized patients but exclude ineligible patients or patients who cancel this study before receiving any protocol treatment.

The primary efficacy endpoint is PFS, which is defined as the time from the date of randomization to the date of earliest radiographic disease progression or death. If the subject does not experience radiographic disease progression or death, then the data will be censored at the date of the last disease assessment. PFS will be analyzed by Kaplan Meier methodology and compared between arm E and arm C, using a log-rank test stratified by disease type (sensitive vs refractory). A two-sided, stratified log-rank test P value will be provided. Median PFS time will be calculated and 95% confidence interval for median PFS will be presented. Overall survival (OS) will be analyzed in a similar manner as PFS.

Late treatment effect is often expected for immunotherapy. For this reason, a weighted log rank test with Harrington-Fleming weights that optimize the expected late treatment effect will be conducted as a supplementary analysis for both PFS and OS. In particular, the following three parameter settings will be used: (1)  $\rho = 0$  and  $\gamma = 0.5$ ; (2)  $\rho = 0$  and  $\gamma = 1$ ; and (3)  $\rho = 0$  and  $\gamma = 2$  (39).

The proportion of subjects with objective response as assessed by the investigator using RECIST version 1.1 will be evaluated for randomized subjects. The objective response rate will be estimated and compared between arm E and arm C, using a Cochran-Mantel-Haenszel (CMH) test stratified by tumor volume. A two-sided, stratified CMH test P value will be provided. In addition, a 95% confidence interval will be constructed for the estimated proportions. Similar analysis will be conducted for disease control rate (DCR), which is defined as the proportion of patients achieving complete, partial and stable disease after the protocol treatment.

All subjects who receive at least one dose of the study drug will be included in safety analysis. Treatment-related toxicity will be summarized by grade, type and system organ

class. Comparisons of the percentages of subjects experiencing an adverse event between arm E and arm C will be performed using Fisher's exact test.

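### The sensitive/refractory objective omits PFS, and Section 20 estimates no effect by disease type for any endpoint

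*Combined protocol and SAP*

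**What the plan says.** Section 6.2, objective iii, reads "Determine the ORR, and OS of pembrolizumab and topotecan, in the following patient groups", and the only grouping under it is sensitive versus refractory disease. PFS is absent, although exploratory objective i in section 6.3 lists ORR, PFS and OS together.

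Section 5.1.1 explains the primary endpoint: "Given the cross-over design, PFS as opposed to overall survival was considered to be an acceptable scientific endpoint". Section 5.1.2 states an expectation about response, that "topotecan leads to a differential response in SCLC patients with sensitive vs refractory disease, which we do not anticipate in those receiving pembrolizumab".

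Section 8.4 names one stratification factor for randomisation, disease type. In Section 20, PFS is compared "using a log-rank test stratified by disease type (sensitive vs refractory". For survival, "Overall survival (OS) will be analyzed in a similar manner as PFS". Response is compared "using a Cochran-Mantel-Haenszel (CMH) test stratified by tumor volume". Neither Section 19 nor Section 20 describes an estimate within sensitive or refractory patients, or a treatment-by-disease-type term, for any endpoint. The sample size in section 19.1 rests on a single effect "in the pooled patient population with relapsed sensitive or refractory SCLC".

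**The concern.** The protocol treats sensitive and refractory disease as different settings. It gives them different survival and different topotecan response rates, randomises by them and sets an objective on them. Three gaps follow.

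- Objective iii has no analysis behind it.
- The only time-to-event endpoint it names is OS. Crossover blurs the arm comparison for OS, and that is the protocol's own reason for making PFS primary.
- The one stated expectation of a differential effect concerns response, and the response test does not use disease type at all.

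If the expectation in section 5.1.2 is right, the pooled treatment effect depends on the mix of patients who happen to enrol, and no quota is stated. A reader would want to see whether the two groups point the same way. Without pre-specified estimates, any such breakdown would be post hoc even though it uses the trial's only randomisation factor.

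**Working it through.** **1. Where disease type enters the plan**

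| Endpoint | In objective 6.2(iii)? | Use of disease type in Section 20 | Estimate by disease type? |
|---|---|---|---|
| PFS | No | Stratifies the log-rank test | None |
| OS | Yes | Stratifies the test, by reference to PFS | None |
| ORR | Yes | Not used; CMH strata are tumor volume | None |

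A stratified log-rank test adjusts for disease type and tests a common effect. It does not estimate whether the effect differs between strata. The ORR test, as written, does not adjust for disease type either.

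**2. The plan's own power figure**

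Inputs from section 19.1: 86 events, HR 0.60, 2:1 allocation, one-sided 0.10. Schoenfeld: z = √(86 × 2/9) × |ln 0.60| − 1.2816 = 4.372 × 0.511 − 1.282 = 0.952, so power is 0.829. With the stated event split (59 of 86) as the allocation it is 0.820. The stated 82% reproduces.

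**3. What PFS by stratum would deliver**

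The documents do not give the share of sensitive patients, so I assume 30% to 70%, with events in proportion. SE(log HR) = 1/√(d × 2/9). For d = 43: 1/√9.556 = 0.3235, CI factor exp(1.96 × 0.3235) = 1.89, and the interval around 0.60 is 0.32 to 1.13.

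| Share of patients in stratum | Events | 95% CI around HR 0.60 | Power, one-sided 0.10 |
|---|---|---|---|
| 30% | 25.8 | 0.26–1.36 | 48% |
| 40% | 34.4 | 0.30–1.22 | 55% |
| 50% | 43.0 | 0.32–1.13 | 62% |
| 60% | 51.6 | 0.34–1.07 | 67% |
| 70% | 60.2 | 0.35–1.03 | 72% |

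**4. PFS interaction**

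The SE of the log ratio of hazard ratios is the square root of the two stratum variances added. Even split: √(2 × 0.1047) = 0.457. A 30:70 split: √(0.1744 + 0.0748) = 0.499. The 95% CI therefore multiplies and divides the estimated ratio by exp(1.96 × 0.457) = 2.45 to exp(1.96 × 0.499) = 2.66. Power for a ratio of 0.5 at two-sided 0.10 is 40% to 45%. Reaching 80% power needs a ratio of about 0.29 to 0.32.

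**5. Response**

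If pembrolizumab response is equal in both groups, the difference between the two treatment effects is the topotecan rate in sensitive minus that in refractory patients. Section 3.1 gives 18% for sensitive patients pooled over three single-arm studies, 3% for refractory patients in one of them, and 37.8% and 6.4% in another. The gap is 15 to 31.4 percentage points.

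With 62 and 31 patients, an even split and pembrolizumab at 32% in both groups (section 19.1's alternative, assumed here per stratum), the SE is √(2 × 0.32 × 0.68/31 + 0.18 × 0.82/15.5 + 0.03 × 0.97/15.5) = 0.159. Power at two-sided 0.10 is 24%. Over sensitive shares of 40% to 60%, the cited topotecan rates and pembrolizumab at 29% to 32%, it runs from 23% to 54%.

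Expected topotecan responders in the refractory stratum number only 15.5 × 0.03 = 0.5 to 15.5 × 0.064 = 1.0. With 15 patients, the chance of none is 0.97^15 = 0.63 to 0.936^15 = 0.37. An ordinary logistic interaction could therefore fail to converge.

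**6. Dependence on case mix (illustration)**

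With topotecan response of 18% in sensitive and an assumed 4% in refractory patients, the pooled control rate is 0.3 × 18 + 0.7 × 4 = 8.2% if 30% are sensitive, and 0.7 × 18 + 0.3 × 4 = 13.8% if 70% are.

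**The case against.** The strongest case against is that this is a 93-patient phase II trial with a pooled primary question, that no passage states an expected PFS difference by disease type, and that the added analyses could not separate the scenarios of interest. The power statement stands: sections 3 to 5 of the working show that only very large differences would be detectable. That limits what may be concluded. It is not a reason to leave the objective without an analysis, since ORR and OS by disease type are already promised under similar limits.

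Four stronger readings might be inferred, and the documents do not support them.

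- *Section 20 ignores disease type.* It does not: the PFS log-rank test is stratified by it, and OS by reference. What is missing is an estimate of the effect in each group.
- *PFS is the only endpoint untouched by crossover.* Section 10.1 allows crossover only after RECIST progression, so response on the randomised drug also precedes it. Section 5.1.2 distinguishes the two settings: "With the cross-over design, we will be able to determine the ORR for pembrolizumab in the second- and third-line setting". Section 20 does not say that the ORR comparison stops at crossover, but of the two endpoints in objective iii only OS is inherently affected.
- *A formal interaction hypothesis goes untested because PFS is missing.* Section 5.1.2 is rationale text about response, and ORR is already in objective iii. That expectation goes unexamined because ORR has no analysis by disease type.
- *A definite multiple for the difference between the groups.* With equal pembrolizumab response, the ratio of odds ratios is the ratio of topotecan odds. Across the rates cited for the three studies (14% to 37.8% sensitive, 2% to 6.4% refractory) it runs from (0.14/0.86)/(0.064/0.936) = 2.4 to (0.378/0.622)/(0.02/0.98) = 30. Those studies also used a 90-day definition, whereas this trial uses 60 days, so the rates are illustrative only.

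**Conclusion.** The point holds as a gap between an objective and its analysis. Objective iii omits the primary endpoint, Section 20 provides no estimate by disease type for any endpoint, and the ORR test is stratified by something other than the randomisation factor. Followed as written, the plan's only time-to-event endpoint by disease type would be the one affected by crossover, and no method is given for it.

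The consequence is limited. The primary test is unaffected and no figure in the plan is wrong on this point. The added PFS results would be imprecise: about 0.32 to 1.13 around HR 0.60 with an even split, and 0.26 to 1.36 for a stratum holding 30% of patients. These figures rest on the planned 86 events, events in proportion to stratum size, and an assumed sensitive share. No firm conclusion by disease type should be drawn from them.

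**What to change.** - **Section 6.2(iii):** list ORR, PFS and OS.
- **Section 20, within each randomisation stratum:** the pembrolizumab versus topotecan PFS hazard ratio with 95% CI and Kaplan-Meier curves; ORR by arm with 95% CI, counting response on randomised treatment before any crossover; and OS, with a note that crossover affects it.
- **Section 20, interaction:** one treatment-by-disease-type estimate with CI for PFS (Cox model) and one for ORR. For ORR, use the risk-difference scale or a penalised logistic model, because the refractory topotecan group may have no responders.
- **Label:** state that all of these are descriptive and not powered, with no significance claim.
- **ORR test:** stratify the CMH test by disease type, or explain the choice of tumor volume and reconcile it with the randomisation factor.

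The cost is a few lines of text and a little programming on data already collected. The downside is wide intervals that could be over-read, which the label is there to prevent.
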